6.3 Study measures: Teacher report

Teacher questionnaires will include the following constructs & measures. While online completion is preferred, teachers may complete surveys via mail, phone, or email, whichever is feasible for the teacher. All assessments will be administered or coordinated by trained staff. Teachers will receive a \$25 incentive for completion. If the teacher is unable to accept the incentive, per their school's policy, study staff will send a gift card to the school's office to use at their discretion.

- a) Child executive function – Child executive function will be collected via teacher report, using the *Behavior Rating Inventory of Executive Function, 2nd edition (BRIEF-2)* as well as select scales in the *Teacher Report form (TRF 6-18)*. The BRIEF-2, ages 6 to 18 years, measures a range of executive functioning capabilities/behaviors in children in the home and school environments. Respondents are asked to record if the described behavior has never, sometimes, or often been a problem for their child in the past 6 months. The selected scales in the TRF (6-18) include: Syndrome Scales (*Anxious/Depressed, Withdrawn/Depressed, Somatic Complaints, Social Problems, Thought Problems, Attention Problems, Rule-Breaking Behavior, Aggressive Behavior*) and DSM-Oriented Scales (*Affective Problems, Anxiety Problems, Somatic Problems, ADHD Problems*,

PROTOCOL TITLE: Long-term Effects and Safety of DHA+AA Supplementation in Toddlerhood for Children born Preterm

Oppositional Defiant Problems, and Conduct Problems). These ask about the child's behavior in the previous six months. Teachers rate the items on a 3-point scale: 0-Not True, 1-Somewhat or Sometimes True, 2-Very True or Often True Assessment time is approximately 15 minutes.

6.4 Source records

Data for this study will include medical record reviews, questionnaires, direct testing/observation of cognitive abilities and behavior, and biospecimens (saliva, blood).

Please see supplemental materials for all applicable source records.

All of the research procedures and questionnaires are designed to meet the definition of "minimal risk" in §45 CFR 46.102(i) and to be reviewed by the IRB under §45 CFR 46.404 "Research not involving greater than minimal risk."

The Principal Investigator will ensure that this study is conducted in full conformity with the principles set forth in The Belmont Report: Ethical Principles and Guidelines for the Protection of Human Subjects of Research of the US National Commission for the Protection of Human Subjects of Biomedical and Behavioral Research and codified in 45 CFR Part 46 and/or the ICH E6; 62 Federal Regulations 25691 (1997). Study staff are also committed to minimizing risks even though they are minimal.

7.0 Data and Specimen Banking

Following collection procedures outlined above (see section 6.2, i and 6.3, l), saliva samples will be stored in a dry, dark secure drawer per [name] instruction, until they are transferred to his team for analysis purposes. All samples will be labeled using de-identified participant identification methods (i.e. assigned, numerical participant study IDs), and will never include participant PHI.

Saliva samples will be transferred to [name] team for analysis. [name] molecular genetics laboratory is experienced in DNA extraction, using protocols his lab developed expressly to maximize the yield of high-quality DNA suitable for genetics assays. DNA from saliva will be maintained after the study is complete and will be stored indefinitely for future analysis and use, per the participant consent document. Specimens may be analyzed for future studies of nutritional and genetic factors in relation to child growth and development. Specimens will be maintained in a secure location in the NCH Center for Biobehavioral Health or Battelle Center for Mathematical Medicine and will be labeled with a numeric code and no identifying information. The numeric code will be linked to the other deidentified study data. Only the study investigators and their staff IRB-approved to work on this research and internal and external human subjects' protection officials and auditors (IRB, FDA, NIH) will have access to the specimens. De-identified study data (but not biospecimens) will be available to scientists external to the study team upon securing appropriate Data Use Agreements and per the informed consent form.

Blood was collected and stored during the original trial from about half of the participants, and these samples have been stored in the [name] Lab - 80°C freezer. The consent form from the original trial included consent for future use of leftover blood. Stored blood from the original trial will be used in lieu of saliva collection if that family provided permission.

8.0 Sharing of Results with Subjects

PROTOCOL TITLE: Long-term Effects and Safety of DHA+AA Supplementation in Toddlerhood for Children born Preterm

Upon completion of the study visit, staff will send a letter to the family that includes the child's generalized results from the standardized testing. This letter will not include specific scores, but will include the range the child scored in (e.g. average, below average, above average). Staff will also explain to families that the testing was completed for research purposes only. Families can contact the study with any questions. [name] is available to assist families in interpreting their letter.

9.0 Study Timelines

9.1 Describe:

Anticipated study enrollment will occur from August 2021 through February 2025. During this time, participants will be invited to participate in a single study visit that lasts 3 hours along with any necessary follow up appointments to address missing or poor quality data. Estimated time for study investigations to complete the study and primary analysis is June 2025.

The duration of an individual subject's participation in the study consists of a single study visit (when child is between 8 years, 180 days and 10 years, 180 days) and any necessary follow-up to address missing or poor quality data.

10.0 Inclusion and Exclusion Criteria

For participation in the original Omega Tots trial, participants met the following inclusion criteria: age 10-16 months (corrected age) at baseline, gestational age <35 completed weeks, discontinued breastfeeding and formula feeding, English language ability adequate to understand the study and its risks. Exclusions: Feeding problem or malformation; metabolic or digestive disorder precluding participation or absorption of the supplement; weight <5th or >95th percentile for corrected age (WHO growth charts); consume a DHA supplement, Pediasure, or fatty fish more than twice per week; plans to leave the area; corn, soy or fish allergy.

The only criteria for the present study are previous participation in Omega Tots, and a current age of 8 years, 180 days to 10 years, 180 days. Our study will include children, their parent or legal guardian, and the child's primary teacher. Any child that is in custody of children's services for their window of eligibility will be excluded. Our study will not include adults unable to consent or prisoners.

11.0 Vulnerable Populations

This study intends to enroll children, a special population, and will accordingly adhere to additional protections specified under 45 CFR Part 46 Subpart D – Additional Protections for Children Involved as Subjects in Research (45 CFR Part 46.401-409). Follow-up at 8½ - 10 ½ years of age was selected because this is a critical developmental period for children born preterm.

PROTOCOL TITLE: Long-term Effects and Safety of DHA+AA Supplementation in Toddlerhood for Children born Preterm

Children (age 8½) may participate in this study under the written informed consent provided by a parent or legal guardian. If children are enrolled at an age ≥ 9 , they will be assented in addition to acquiring caregiver informed consent. This study does not include any other vulnerable populations (i.e. adults unable to consent or prisoners). Parents/guardians who may be pregnant at the time of enrollment will be invited to participate as their pregnancy is in no way related to the study intervention. Children of a parent who is cognitively impaired or mentally ill are not eligible if the parent is not able to understand fully the research project and to grant informed consent.

12.0 Local Number of Subjects

We hope to enroll as many of the eligible 377 caregiver-child dyads as possible for the current study.

13.0 Recruitment Methods

13.1 Procedures

To recruit families, an attractive “mailer box” will be sent to all eligible families. Mailer boxes will be addressed to the child and their family, and include: child-friendly details such as a greeting card; a small, engaging gift or activity (e.g. sensory keychain or craft kit); an introductory letter (signed by the PI) that describes the child’s previous participation and offers related details about the new study; and an attractive, professionally-designed study brochure that provides additional information about the research team.

Prior to the mailer box being sent, a Recruitment and Retention (R&R) Specialist will ensure that the child is not deceased or in the care of Children’s Services by verifying this information in EPIC. R&R Specialists will reach out to families (via phone call/text/email). Approximately 1 week post-mailer, the R&R Specialist will reach out to families (via call/text/email) to further describe the study and gauge child and caregiver interest. Participation or refusal to participate in the study will not affect entitlement to clinical care. Study visits will be scheduled at convenient times and with additional services as needed. Families will be reminded of scheduled/upcoming appointments via phone, email and/or text (based on family preference). Attempts will be made via phone, email, text, and/or mail to contact families who do not show for their scheduled visits. Non-responsive or “hard to reach” families will be contacted with further, well-honed attempts by the R&R Specialist. Examples of this include using the child’s electronic medical record (e.g. EPIC) to retrieve up-to-date contact information, connecting with families at an upcoming clinical care appointment, a web-based online search service (e.g., <http://www.whitepages.com/>) that gathers information through public records, similar to a Google search. The search service provides a fast and effective way to look-up or verify contact information about a person, phone number or address of interest. Additional methods to contact hard to reach families may include contacting additional contacts provided during the Omega Tots trial to aid in identifying updated contact information (postal mail, phone). If the additional contact listed for the caregiver also has outdated contact information, attempts will be made to reach them using the same web-based online search service (e.g., <http://www.whitepages.com/>). Before contact is made with each eligible family, life (or death) status of the caregiver and child will be affirmed using the child’s electronic medical record (EPIC) as well as through vital records maintained by the Ohio Department of Health.

Families who have not enrolled or refused participation by March 18, 2024 will be sent an additional mailer box. Mailer boxes will be addressed to the child and their family and include: a small gift for the

PROTOCOL TITLE: Long-term Effects and Safety of DHA+AA Supplementation in Toddlerhood for Children born Preterm

child and their caregiver; a flyer that succinctly describes the child's previous participation, details about the new study, and options for participation; and a brochure that provides additional information about the study. Prior to the new mailer box being sent, a R&R Specialist will re-confirm that the child is not deceased or in the care of Children's Services by verifying this information in EPIC. Approximately 1 week post-mailer, R&R Specialists will reach out to the families in the same manner as the initial recruit attempts. Families who are still non-responsive after these attempts will receive a packet containing: a flyer that briefly describes participation options, QR codes to the study survey and refusal questionnaire, paper copies of the survey and refusal questionnaire, study information sheet, saliva collection kits and a pre-paid return envelope.

Children and a parent/guardian will come to NCH when the child is between 8 years, 180 days to 10 years, 180 days and provide written consent/assent. If the parent is interested in enrolling and the child is in the age range, the study staff will guide the parent and child through the process. Teacher recruitment will begin following family enrollment. The caregiver will fill out the "Release of Information Teacher Form," which permits study staff to contact the child's school and teacher, and staff may follow up with caregivers to affirm child's current teacher if visits occur during summer months.

Participants will be recruited from the original Omega Tots cohort (n=377). No additional sources or subject identification methods are necessary.

13.2 Describe materials that will be used to recruit subjects. (Attach copies of these documents with the application.)

Please see supplemental materials for recruitment materials.

13.3 Describe the amount and timing of any payments to subjects.

N/A- Participants will receive compensation following completion of the in-person study visit (see section 6.1 for details).

14.0 Withdrawal of Subjects

14.1 Procedures

As this is a prospective cohort design with no new investigational drugs or products, we do not anticipate many circumstances under which subjects will be withdrawn from the study without their consent. If the PI feels it is in the interest of the child or parent/guardian to not enroll them or to discontinue data collection with them prematurely, the PI will make that decision. We also do not see the need for any procedures regarding orderly termination from the study.

However, we recognize that research participation is completely voluntary; subjects may choose to withdraw consent/assent at any time. Should a participant indicate they would like to formally withdraw from the study, they will be asked to connect with the Principal Investigator (PI), Study Coordinator, or trained research staff via phone (or if currently at a study visit, in person).

If the research participant wishes to withdraw or refuses participation in the study, the staff will attempt to complete a "refusal questionnaire" with the family, to document their main reason in writing, and to

PROTOCOL TITLE: Long-term Effects and Safety of DHA+AA Supplementation in Toddlerhood for Children born Preterm

collect a few additional details about families that withdraw or refuse withdraw (e.g. any participation barriers, etc.). Some families may refuse this questionnaire; if so, staff will refrain from completing it.

If the participant wishes to withdraw all previously submitted data/PHI from the study, in addition to discontinuing future participation, the participant will be asked to submit this request in writing via mailed letter to the Principal Investigator ([name]). [name] updated address will be included in the informed consent/assent documents, but will also be offered again at the time of withdraw procedures if needed by the participant. If a subject also wishes to have their DNA withdrawn, then [name] will destroy the DNA sample using appropriate molecular methods.

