2.1 Hypotheses & Aims

Our central hypothesis is that preterm children who were randomized to 180 days of DHA+AA at age 1 will exhibit poorer general cognitive ability, greater language deficits, and more impaired executive function at age 8½ -10½ vs children randomized to placebo. Our hypothesis has been formulated primarily on the findings from Omega Tots and DINO, the largest DHA-supplementation trial of preterm infants. The rationale for this project is that a careful examination of the long-term effects of DHA+AA supplementation will offer much-needed clarification about the appropriateness of DHA+AA as an intervention to promote neurodevelopment among children born preterm. We plan to pursue our central hypothesis and accomplish our objective by pursuing the following specific aims:

Aim 1: Determine the long-term effect of DHA+AA supplementation at age 1 year by comparing general cognitive ability, language, and multiple facets of executive function between the DHA+AA and placebo arms at age 8-9.

- Based on our preliminary data, working hypothesis 1 is that children randomized to DHA+AA at age 1 will display at least a 0.3-SD (effect size) deficit on measures of general cognitive ability, language, executive function at age 8½ - 10½ vs placebo.
- Sub-aim 1: Explore sub-group differences by sex, birthweight, socioeconomic status, and diet.

PROTOCOL TITLE: Long-term Effects and Safety of DHA+AA Supplementation in Toddlerhood for Children born Preterm

Aim 2: Determine the role of variability in fatty acid metabolism genetics en masse on the effect of DHA+AA supplementation on short and long-term outcomes, and further focus on 2 previously published FADS2 genetic variants.

- Based on prior observational studies, working hypothesis 2a is that common genetic variant-based heritability over long-chain fatty acid metabolism will be associated with poorer performance on our outcome assessments at ages 1, 2, and 8½ - 10½ years for children assigned to DHA+AA vs placebo. Genetic variation is based on measured SNPs in genes accounting for virtually all synthesis of very long-chain fatty acids. Further, we hypothesize (2b) that minor allele status for FADS2 rs1535 and rs174575, the most commonly replicated SNPs in the literature, will be associated with poorer outcomes for children assigned to DHA+AA, vs placebo.

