6.0 Procedures Involved*

6.1 Study Design

This is a prospective cohort, built from our randomized, blind, placebo-controlled Omega Tots trial of DHA+AA supplementation for 180 days involving children 10-16 months of age (adjusted for prematurity) at enrollment. Participants are Nationwide Children's Hospital (NCH; Columbus, OH) former NICU patients born at <35 weeks' gestation (n=377). All 377 randomized children will be eligible for in-person follow-up at age 8½ - 10½, even those with missing data from the trial, per intent-to-treat. All investigators (except the Principal Investigator and biostatistician), study staff, clinic staff, parents, and children will remain blind to the child's treatment assignment.

The cohort study will be conducted at NCH. There are no collaborating sites where enrollment or data collection will be performed. To recruit families, an attractive "mailer box" will be sent to all eligible families. A Recruitment and Retention (R&R) Specialist (part of the study team at NCH) will call families approximately 1 week post-mailer to further describe the study and gauge child and caregiver interest. Non-responsive or "hard to reach" families will be contacted with further, well-honed attempts by the R&R Specialist. Participation or refusal to participate in the study will not affect entitlement to clinical care.

Children and a parent/guardian will come to NCH when the children are between 8 years, 180 days and 10 years, 180 days, and provide written consent/assent. It is expected that participant enrollment will begin by August 2021, and that human subjects' activity will be completed by February 2025.

Visits will occur in the Center for Biobehavioral Health, child-friendly observation rooms (x8) with video recording equipment built for assessment, observation, and interviews. Trained, experienced staff will carry out the visits 7 days/week including evenings for family convenience. Proposed visit length is approximately 161 minutes.

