17.2 Data quality, storage, and security

Subject confidentiality is strictly held in trust by the participating investigators, their staff, and the sponsor(s) and their agents. The study protocol, documentation, data, and all other information generated will be held in strict confidence. No information concerning the study or the data will be released to any unauthorized third party. The IRB or other authorized representatives may inspect all documents and records required to be maintained, including but not limited to, data collection records for the subjects in this study. Records will be retained indefinitely, and safeguarded using password protected and encrypted devices (computers, cell phones) and through de-identification processes during storage, use, and transmission.

Questionnaire data and scores from some neuropsychological tests will be entered directly into a secure iPad using REDCap, a customizable data collection and study management tool suited to computer-

PROTOCOL TITLE: Long-term Effects and Safety of DHA+AA Supplementation in Toddlerhood for Children born Preterm

assisted in-person collections which we have used in many studies. The Toolbox and other computerized assessments have their own secure interfaces and back-end databases for data storage. The Clinical Research Coordinator and PI will assure quality by observing a sample of data collections, restricting entry of and checking for out-of-range values, and staff refresher training. The NCH Research Data and Computing Core will provide REDCap support to design and manage the databases and will maintain secure server storage backed up nightly.

The study staff is also responsible for data management, quality review, analysis, and reporting of the study data under the direction of the investigator team. Paper study records will be kept in secure, locked locations in the NCH Center for Biobehavioral Health (CBH). Electronic files will be maintained at NCH. Electronic REDCap databases will be housed on the secure networked server at NCH and only accessible to study staff from NCH. Participant names and contact information will be stored separately from participant data (identified by code number only) and only be accessible to key personnel. Original source documents will be maintained indefinitely.

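### The unblinded Principal Investigator (PI) makes discretionary decisions on non-enrolment and early end of data collection; blinded staff should make them, with counts logged by arm

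*Combined protocol and SAP*

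**What the plan says.** - **Who knows allocation.** Protocol 6.1: "All investigators (except the Principal Investigator and biostatistician), study staff, clinic staff, parents, and children will remain blind" to the child's assignment. The PI and the biostatistician are the only exceptions.
- **Direction of the hypothesis.** Protocol 2.1 predicts that "preterm children who were randomized to 180 days of DHA+AA at age 1 will exhibit poorer general cognitive ability" than placebo children, and that the DHA+AA group "will display at least a 0.3-SD (effect size) deficit on measures of general cognitive ability", language and executive function.
- **Discretion over who contributes data.** Protocol 14.1 opens with a condition, "If the PI feels it is in the interest of the child or parent/guardian", and continues "to not enroll them or to discontinue data collection with them prematurely, the PI will make that decision". The same section adds that "we do not anticipate many circumstances under which subjects will be withdrawn from the study without their consent".
- **Data quality.** Protocol 17.2: "The Clinical Research Coordinator and PI will assure quality by observing a sample of data collections", together with restricting and checking out-of-range values and refresher training for staff.
- **Repeat contact.** Protocol 9.1 allows "any necessary follow-up to address missing or poor quality data" and does not say who judges quality.
- **Eligibility and recruitment.** Section 10.0 limits the criteria to earlier trial participation and the age window, with an exclusion for children in the custody of children's services. Section 13.1 gives record checks and family contact to the Recruitment and Retention Specialists, and consent to study staff.

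**The concern.** Blinded testers protect the scoring of a test. They do not protect the choice of who is tested, whose visit is cut short, or whose result is queried. Under 14.1 that choice can fall to someone who knows the arm and works under a hypothesis of harm. It rests on a personal judgement, with no written criteria and no blinded second opinion.

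No bad faith is needed, and the bias could run either way. Someone who believes the supplement did harm might more readily spare a struggling DHA+AA child from testing, which would hide harm. Ending testing more readily for a struggling placebo child would exaggerate it. The study is meant either to reassure families or to flag lasting harm, so an error in either direction matters.

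The analysis in 17.1 gives limited protection. Intent to treat keeps a child in the assigned arm but cannot supply an age 8½–10½ score that was never collected. The maximum-likelihood model assumes that such scores are missing at random.

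**Working it through.** **Step 1. Set the sections side by side.** 6.1 (PI unblinded) and 14.1 (PI decides) establish that an unblinded person holds this discretion. 17.2 adds a role in quality checks, shared with the Coordinator. 9.1 names no decision maker, so it shows a gap and not a PI power. No section adds a blinded decision maker or a log by arm.

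**Step 2. Reproduce the plan's figure.** Section 17.1 claims more than 80% power for 0.32 SD with 300 children split equally at alpha 0.05. Sidedness is not stated, so two-sided is assumed.

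- Power = Φ(0.32 × √(150/2) − 1.96) = Φ(2.771 − 1.960) = 0.791. A two-sample t-test gives 0.789.
- Sample size for 80% power = 2 × (1.960 + 0.842)² / 0.32² = 153.3, so 154 per arm.

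The figure is reproduced to within about one percentage point, just under the stated level. Nothing below depends on that difference.

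**Step 3. Size the route to bias.** The documents give no count of PI decisions, so k and m are assumptions. Suppose k of 150 children in one arm only, each m SD from that arm's mean on the same side, are not assessed, and there is no true effect.

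- Shift in the arm mean: δ = k × m / (150 − k).
- Standard error in SD units: SE = √(1/150 + 1/(150 − k)).
- Two-sided type I error: 1 − Φ(1.96 − δ/SE) + Φ(−1.96 − δ/SE).

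Example with k = 5 and m = 2: δ = 10/145 = 0.0690; SE = 0.1165; δ/SE = 0.592; error = 0.0857 + 0.0054 = 0.091.

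| k | m (SD) | δ (SD) | δ / 0.32 | Type I error |
|---|---|---|---|---|
| 1 | 1 | 0.0067 | 2.1% | 0.0504 |
| 1 | 2 | 0.0134 | 4.2% | 0.0515 |
| 2 | 1 | 0.0135 | 4.2% | 0.0516 |
| 2 | 2 | 0.0270 | 8.4% | 0.0563 |
| 5 | 1 | 0.0345 | 10.8% | 0.0601 |
| 5 | 2 | 0.0690 | 21.6% | 0.0910 |
| 10 | 1 | 0.0714 | 22.3% | 0.0933 |
| 10 | 2 | 0.1429 | 44.6% | 0.2291 |

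This simple comparison ignores baseline adjustment and family clustering, and it holds the SD at 1.

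**Step 4. Would the model repair it?** If a decision depended only on arm and the recorded baseline, the missing-at-random assumption could still hold. If it depended on arm and on an unrecorded impression of how the child would perform, the assumption fails and the model leaves the shift in place.

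**The case against.** The case against is substantial and narrows the point.

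- **It is a welfare clause.** The power arises only when the PI judges it to be in the family's interest, and few uses are expected. A reader might infer that the PI screens the cohort. The documents do not support that: all 377 children are eligible (6.1), as many as possible are to be enrolled (12.0), and contact and consent are handled by study staff, who are blinded.
- **The quality role is limited and shared.** Range checks catch impossible entries and give little scope to choose among plausible scores. Computerised tests write to their own databases. Nothing in 17.2 lets the PI void a session or delete a score.
- **PI control of repeat testing is inference.** A reader might combine 9.1 with 17.2 and conclude that the PI decides who is retested. 9.1 names nobody.
- **The larger losses are constructed.** Five or ten losses, all in one arm and all in the same direction, have no basis in the documents. Before enrolment the PI would not have the child's age 8½–10½ scores to select on.
- **The PI has oversight duties.** Section 6.4 makes the PI responsible for ethical conduct, and 15.1 puts safety oversight under the PI's direction. Barring the PI from all observation until database lock would cut across both.

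All of this stands. What remains is that, when the discretion is used, an unblinded person uses it on a subjective test with no record by arm.

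**Conclusion.** The point holds as a procedural weakness that is cheap to remove. The documents show a possible route to bias; they do not show that bias has occurred or that it is likely to be large.

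One decision moves an arm mean by about 0.01 SD and leaves type I error at 0.050 to 0.052. The effect becomes material only at about 5 to 10 decisions, all in one arm and in the same direction: 0.03 to 0.14 SD, or 11% to 45% of the 0.32-SD target, with type I error of 0.06 to 0.23. That range rests on assumed counts, 150 children per arm, losses 1 to 2 SD from the mean, and no true effect. Given the plan's own expectation of few cases, the realised bias is probably small and may be zero. Without a log by arm, a reader of the results could not confirm this.

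**What to change.** - **14.1:** a named blinded co-investigator makes discretionary decisions not to enrol a child or to end data collection early. The PI keeps overall and urgent safety oversight, consistent with 6.4 and 15.1.
- **17.2 and 9.1:** state that any judgement that a session is invalid or needs repeating is made by blinded staff.
- **Record:** log every such decision with its date and reason, and report counts by arm with the primary results. If visits are already complete, compile the counts from study records and report them.

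**Cost:** a wording amendment, a small change in the PI's role and minor extra record keeping. Blinded co-investigators already exist (6.1), and section 25.0 describes the investigators as close to one another and flexible in their availability. The welfare safeguard is kept, because a blinded investigator can make the same judgement.
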